3.2 Allocation to Treatment Groups

The initial mode of ventilation will be randomly assigned using a computer-generated sequence. Investigators and clinicians will not be blinded to the ventilator mode as it is essential for medical management. Every subject will be placed in both ventilator modes during the study to serve as their own controls.

3.3 Study Duration, Enrollment and Number of Sites

3.3.1 Duration of Study Participation

The duration of the interventional phase of the study will be up to 11 days per subject, with 1 day in observation, 5 days in the initial ventilator mode, and 5 days in the second ventilator mode. All subjects will be followed until discharge for safety and assessment of the postmenstrual age and respiratory support administered at discharge.

3.3.2 Total Number of Study Sites/Total Number of Subjects Projected

The study will be conducted in two intensive care units at CHOP (NI/ICU and PICU) and the PICU at Hasbro Children's Hospital.

Recruitment will stop when 20 subjects successfully complete the trial. It is expected that approximately 25 subjects will be enrolled to produce 20 evaluable subjects.

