Safety Evaluations	Subject safety will be monitored by through assessment of adverse events, vital signs, physical examinations, and laboratory data by the medical and study teams as well as the independent data safety monitoring committee. All study investigators and a core group of respiratory therapists who will care for study infants will be provided training on the Servo I ventilator and the NAVA mode. Clinicians responsible for the care of study subjects receiving the NAVA mode of ventilation will be trained up to the current standard for their role, as is done for clinicians using clinically deployed ventilators. Guidelines for startup and continued management, including troubleshooting techniques of the NAVA mode, will be available for the medical teams and a study investigator will be on call 24/7. Individual subjects will be withdrawn from the study for safety if there is an absolute, sustained increase in FiO ₂ by 20% or if the pCO ₂ /TcO ₂ increase by 25 points above baseline or to a level greater than 90 mm Hg, for more than 2 hours while on the NAVA mode. If this occurs, the patient will discontinue NAVA therapy and be transitioned to previous CMV settings. A study investigator will round daily with the clinical team and be available 24/7 for questions. The overall safety of the study will be assessed with interim safety analyses after the completion of every 5 patients (3 times total) and in the event of any serious safety events.
Statistical and Analytic Plan	Summarized values for the primary and secondary outcomes will be compared between the two treatment arms using paired statistical tests (e.g. Wilcoxon signed rank tests, paired t-tests) as appropriate, based on the data distribution. Linear mixed effects models will be used to explore longitudinal change in the study outcomes (as continuous measures) as a function of the treatment arm.
DATA AND SAFETY MONITORING PLAN	Clinical adverse events will be monitored throughout the study period. There will be monthly and as needed ad-hoc study investigator meetings to discuss and monitor trial data and safety. All data will be kept confidential in accordance with HIPPA and CHOP policies. An independent safety monitoring committee inclusive of physicians from each study site will be formed to review any adverse events, adjudicate relatedness to the study procedures, and recommend trial continuation or early closure.

TABLE 1: SCHEDULE OF STUDY PROCEDURES

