5.2 Safety Evaluation

Subject safety will be monitored by adverse events, vital signs, physical examinations, and laboratory data by the medical and study team as well as the independent safety monitoring committee.

Clinicians responsible for the care of study subjects receiving the NAVA mode of ventilation will be trained up to the current standard for their role, as is done for clinicians using clinically deployed ventilators (as listed in section 8.4.2). Guidelines for startup and continued management, including troubleshooting techniques, of NAVA mode will be available for the medical teams and a study investigator will round with the clinical team daily to provide expertise on the device/mode as well as be on call for assistance 24/7. Individual subjects will be withdrawn from the study for safety if an absolute increase in FiO_2 by 20% or if the $\text{pCO}_2/\text{TcO}_2$ increase by 25 points or greater than 90 mm Hg, which ever is achieved first, for more than 2 hours from baseline while on NAVA mode, The NAVA arm of the study will be discontinued and the patient will be transitioned to previous CMV settings. Study investigators will be available 24 hours day when a patient is on the trial.

The overall safety of the study will be assessed with interim safety analysis after the completion of every 5 patients (3 times total) and upon any serious safety events occurring.

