6.3 Statistical Methods

6.3.1 Analysis Plan

Subject demographic and clinical characteristics will be summarized with standard descriptive statistics. Summarized values for the primary and secondary outcomes will be compared between the two treatment arms using paired statistical tests (Wilcoxon signed rank tests, paired t-tests) as appropriate based on the data distribution. Crossover treatment trials traditionally have a washout phase with no treatment in order to determine if all outcome measures are reflective of the current treatment and not remnants of the prior treatment. Ventilation studies are not able to have a washout phase, as it is not possible to stop providing ventilator support for a set timeframe. In addition, the timeframe needed for

a washout is unknown for change in ventilation modes. For the primary analysis, all data will be included in the analysis. As a secondary analysis we will selectively exclude the first 4, 8, and 12 hours of data to determine what washout phase may make a difference in data analysis. This timeframe will be considered a washout out phase to ensure all data collected for each mode of ventilation is related to this mode and not residual effect of the prior mode. Linear mixed effects models will be used to explore longitudinal change in the study outcomes (as continuous measures) as a function of the treatment arm. These models are well suited for repeated measurements in longitudinal studies and are capable of handling unbalanced data if present (e.g. due to drop-out). Random effects terms for both the intercept and slope will be evaluated to account for potential subject specific deviation from the cohort's overall average baseline (intercept) and change over time (slope). Model fit will be assessed using the Akaike Information Criterion.

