6.4 Sample Size and Power

We will enroll up to a total of 25 subjects to generate 20 subjects will have adequate evaluable data, during a proposed 24 month study period. The **Table** shows the number of patients required, with 80% power and $\alpha=0.05$, to detect a range of within subject differences in mean oxygen saturation index (at various within subject standard deviation [SD] levels) between the two treatment periods. As shown, the proposed sample size of 20 subjects will provide sufficient power to detect a range of clinically meaningful differences in oxygen saturation indices with statistical significance.

Table. Minimal detectable difference in mean oxygen saturation index

SD	Detectable difference			
	1	1.5	2	3
0.25	4	3	3	3
0.5	7	5	4	3
1	18	10	7	5
1.5	38	18	11	7
2	65	30	18	10
3	144	65	38	18

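### Recruiting to 20 completers, with a numeric deterioration exit only on NAVA and no rule for analysing exits, can tilt the paired comparison toward NAVA

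*Combined protocol and SAP*

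**What the plan says.** **Recruitment.** Section 3.3.2: "Recruitment will stop when 20 subjects successfully complete the trial". Section 6.4: "We will enroll up to a total of 25 subjects to generate 20 subjects will have adequate evaluable data". Neither successful completion nor evaluable data is defined.

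**Primary comparison.** Section 6.3.1: "Summarized values for the primary and secondary outcomes will be compared between the two treatment arms using paired statistical tests". On which data enter, the nearest statement is "For the primary analysis, all data will be included in the analysis", made while discussing washout hours. Drop-out is mentioned only for the exploratory mixed models.

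**Exit.** Section 5.2 opens the rule with "Individual subjects will be withdrawn from the study for safety", gives FiO2 and CO2 thresholds, and limits them to changes lasting "for more than 2 hours from baseline while on NAVA mode". It then adds: "The NAVA arm of the study will be discontinued and the patient will be transitioned to previous CMV settings". The synopsis (Safety Evaluations) has the same structure: withdrawal from the study, then "If this occurs, the patient will discontinue NAVA therapy and be transitioned to previous CMV settings". No numeric rule is given for CMV. Section 4.3 allows discretionary withdrawal in either mode, and section 8.4.2 adds an option, for the CHOP site, to leave NAVA for the standard ventilator.

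**Outcome.** OSI is mean airway pressure times FiO2, divided by SpO2 (6.1). FiO2 is therefore both an exit trigger and a factor of the outcome; CO2 is not part of OSI.

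**The concern.** A paired test needs a value from each period. If a NAVA exit ends participation, a NAVA-first subject has no CMV period and cannot form a pair. A NAVA-second subject has a full CMV period and a shortened NAVA period, and may be judged not evaluable. Under the 3.3.2 rule each lost subject is replaced by one who got through NAVA.

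Losses of this kind are not random. Where exits are linked to high OSI on NAVA, the 20 completers are selected for lower NAVA-period OSI, with no matching numeric rule acting on CMV. The trial tests a reduction in OSI at p<0.05 (2.1) and is meant to supply pilot data on safety and efficacy (section 2). Losing subjects who did badly on NAVA would flatter the first and understate a disadvantage relevant to the second.

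**Working it through.** **1. The plan's own figures.** A two-sided paired t-test at 0.05, with SD of the difference = √2 × within-subject SD, reproduces all 24 cells of the 6.4 table. Example: SD 1, difference 1, n = 18 gives noncentrality (1/√2) × √18 = 3.0 and power 80.7%; n = 17 gives 78.1%. The enrolment figure is 20/(1 − 0.20) = 25. The sample size is sound; the question is who makes up the 20. Results below are in the table's within-subject SD.

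**2. Assumptions.** Exit rate p on NAVA is 5-20%; correlation ρ between the exit trigger and NAVA-period OSI is 0 to 1; no true difference; 1:1 sequence; enrolment until 20 pairs. The documents give neither p nor ρ.

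**3. Expected shift among those analysed.** With a normal trigger, z the upper-p point and φ the normal density:

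- all exits lost: shift = −ρ × φ(z)/(1 − p)
- only NAVA-first exits lost: shift = −ρ × ½φ(z)/(1 − p/2)

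At p = 0.20, φ(0.842) = 0.280, giving 0.280/0.80 = 0.350ρ and 0.140/0.90 = 0.156ρ. At p = 0.10, φ(1.282) = 0.1755, giving 0.195ρ and 0.092ρ. At p = 0.05, φ(1.645) = 0.1031, giving 0.109ρ and 0.053ρ.

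**4. Simulation** (60,000 trials per cell). Each entry is the shift toward NAVA in SD, then the two-sided error, at ρ = 0.5 / ρ = 1.0.

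| Exits | Only NAVA-first lost | All lost |
|---|---|---|
| 4% (one in 25) | 0.02 / 0.04; 4.9 / 5.1% | 0.04 / 0.09; 5.2 / 5.7% |
| 5% | 0.03 / 0.05; 5.0 / 5.1% | 0.05 / 0.11; 5.4 / 6.1% |
| 10% | 0.05 / 0.09; 5.2 / 5.8% | 0.10 / 0.19; 6.0 / 9.2% |
| 20% | 0.08 / 0.16; 5.4 / 7.6% | 0.18 / 0.35; 8.4 / 21.0% |

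At ρ = 0.2 the shift is 0.01-0.07 SD and the error 4.9-5.6%. At ρ = 0 there is no shift.

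**5. How many losses this takes.** With all exits lost, 20% means 20/0.80 = 25 enrolled and five lost; 5% means 20/0.95 ≈ 21 enrolled and one lost. With only NAVA-first exits lost at 20%, 20/0.90 ≈ 22 are enrolled and about two lost. At 20% with all lost, the chance that 25 enrolled yield fewer than 20 completers is P(Bin(25, 0.8) ≤ 19) = 38%, so many such trials could not reach 20 within the plan's ceiling. The shift formula does not depend on n; the error rate does.

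**6. Offsetting CMV withdrawals.** With 20% NAVA exits and 10% outcome-related CMV withdrawals, all lost, at ρ = 1: 0.350 − 0.195 = 0.155 SD (simulated 0.154; 0.079 at ρ = 0.5). If only first-period exits are lost, 0.03-0.06 SD remains. Equal rates leave 0.

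**7. Finer time scale.** Each 5-day period was modelled as 60 two-hour blocks (5 × 24/2), autocorrelation 0.8-0.98, with exit at the first threshold crossing. At 20% exits, completers only, the shift is 0.08-0.15 SD at ρ = 0.5 (false NAVA benefit 5-7%, nominal 2.5%) and 0.16-0.32 SD at ρ = 1 (9-18%). With independent periods, keeping the shortened NAVA-second data while losing NAVA-first exits leaves 0.00-0.05 SD at ρ = 0.5 and 0.00-0.12 SD at ρ = 1. Comparing all 25 by assigned period gives a shift within 0.01 SD of zero and error 4.2-5.5%.

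**The case against.** The strongest reply is that the effect may be very small. The exit needs little more than two hours of deterioration, whereas OSI is summarised over five days; CO2 exits need not involve OSI; and discretionary withdrawal under 4.3 can remove CMV subjects too. All of this stands, and it is why the range starts at zero.

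A second reply is that the plan already covers the matter. It does so only in part. Including all data may keep a shortened NAVA period but cannot supply a CMV period that never took place. The mixed models are exploratory and are not the primary test. Blinded analysis (8.1.1) does not decide who is analysed.

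Stronger readings are tempting but not supported:

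- *That the plan excludes exits, or that its error rate is 21%.* It never says that exits are excluded; it leaves the point open. The 21% needs 20% exits, all lost and all driven by OSI.
- *That false NAVA benefit could reach 46%.* Five exits chosen on the NAVA-minus-CMV difference itself would give that, but the rule measures change from baseline, not from the CMV period.
- *That the synopsis and 5.2 contradict each other.* They agree; the tension between leaving the study and leaving NAVA lies within each of them.
- *That post-exit OSI will be available anyway.* The record review to discharge is planned for age and respiratory support at discharge (3.1.2, 3.3.1).

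**Conclusion.** The concern holds in conditional form. The recruitment rule, the paired test and the NAVA-only numeric exit together allow NAVA failures to be replaced by completers, and nothing in the plan prevents it. The direction favours NAVA whenever exits track NAVA-period OSI and are not matched by similar CMV losses.

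Under the assumed ranges the spurious benefit is 0 to about 0.16 SD if only NAVA-first exits are lost (two-sided error about 5-8%) and 0 to about 0.35 SD if all are lost (about 5-21%). At SD 1 the extreme is 0.35 OSI units, about a third of the smallest difference in the 6.4 table. That extreme needs about five OSI-driven NAVA losses. One exit in 25 gives at most 0.09 SD and 5.7% error; correlation near zero, or similar outcome-related CMV withdrawals, leaves essentially nothing. The gap in the text is certain; its size is not. It should be closed before analysis because closing it is cheap.

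**What to change.** Leave the clinical exit rule unchanged.

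1. Within both the synopsis and 5.2, reconcile withdrawal from the study with stopping NAVA and returning to CMV. State whether follow-up and the other period continue.
2. Unless consent is withdrawn, continue recording the already-charted OSI (the 4-6 hourly values in 6.2) to day 11 after an exit. Say so explicitly.
3. In 6.3.1, define the primary analysis set as all randomised subjects and compare OSI by assigned period (days 2-6 against days 7-11), including post-exit data. State how a subject who never starts NAVA is handled; a CMV-first subject withdrawn before NAVA would otherwise contribute a CMV-against-CMV pair. As sensitivity analyses, use NAVA data up to exit only, and give NAVA exits the worst rank. Report exits by mode and period.
4. In 3.3.2 and 6.4, count recruitment by subjects randomised instead of successful completers, within the ceiling of 25 enrolled. Randomising exactly 25 is not required: enrolment precedes the observation day, so any loss before randomisation would push enrolment past 25, and with few exits a fixed 25 would expose more infants than the present rule (about 21 at 5% exits, all lost).

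**Cost.** Mainly wording, plus continued extraction of charted values. The statistical price, which the plan should state, is dilution that grows with exits. In the block model a true 1 SD benefit is estimated as 0.94-0.99 SD, with power 78-85% at 20 randomised and 87-92% at 25, against 85% for 20 complete pairs. A true 0.5 SD harm appears as 0.47-0.48 SD when the exit rate without harm is 5%, and about 0.38-0.43 SD when it is 20%. Completers only show 0.31-0.46 SD and about −0.04 to 0.38 SD respectively. The sensitivity analysis cut at exit is itself biased against NAVA, by 0.02-0.16 SD at 20% exits.

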3.4 Study Population

3.4.1 Inclusion Criteria

- 1) Gestational ages (GA) \leq 32 weeks
- 2) Current age between 36 weeks postmenstrual age (PMA) and 2 years corrected age
- 3) Severe BPD (as per NIH consensus definition) diagnosed at 36 weeks postmenstrual age
- 4) Receiving invasive mechanical ventilation for ongoing lung disease
- 5) Not expected to be ready for extubation within 11 days following enrollment
- 6) Parental consent

3.4.2 Exclusion Criteria

- 1) Severe congenital anomalies
- 2) Known diaphragmatic defect
- 3) Current treatment with high frequency mechanical ventilation
- 4) DNR Status or Futility of Care
- 5) $>10\%$ leak around the artificial airway,
- 6) Treatment with neuromuscular blockade within 72 hours prior to enrollment
- 7) Acute respiratory instability defined as a ventilator rate increase > 15 bpm, PEEP increase > 2 cm/H₂O, sustained FiO₂ increase $> 20\%$, and/or prescribed increase in tidal volume > 2 mL/kg within 24 hours prior to enrollment will be excluded.

Subjects that do not meet all of the enrollment criteria may not be enrolled. Any violations of these criteria must be reported in accordance with IRB Policies and Procedures.

4 STUDY PROCEDURES

4.1 Screening and Commencement of Study

The following evaluation will be done prior to the study:

- Informed Consent
- Medical Record Review

4.2 Unblinded Ventilator Mode Crossover Phase

Observation phase and Ventilation Mode crossover phases will have the same study procedures performed on a daily basis or less frequently as indicated.

- Placement of NAVA catheter. Catheter will be placed prior to the baseline monitoring phase and will be replaced before going into the 2nd ventilator mode on day 7 of the study.
- Placement of transcutaneous CO₂ monitor (Tcom) (if not already in use) will occur prior to the monitoring phase and remain throughout the 11 days of data collection.
- Salivary cortisol samples will be collected three times per day using a swab placed in the patient's mouth to collect pooled saliva. Samples will be collected at the same time each day and independently analyzed for cortisol values. The 3 cortisol values will be averaged for the 24 hour time frame.
- Asynchrony index will be calculated as the number of asynchrony events divided by the sum of the ventilator cycles and ineffective efforts for 1 minute. This will be determined two ways: first by physical assessment by the respiratory therapist with their patient/ventilator assessments every four hours and second by assessment of time delay or complete miss of neural trigger compared to ventilator trigger from ventilator waveforms.
- Download of data from the ventilators and clinical monitoring equipment as well as extraction of information from the electronic medical record will be done for data normally documented as part of routine clinical care.

4.3 Subject Completion/Withdrawal

Subjects may withdraw from the study at any time without prejudice to their care. They may also be discontinued from the study at the discretion of the Investigator or attending physician to protect the subject for reasons of safety or for administrative reasons. If the withdrawal occurs during the NAVA mode phase of the trial, each site will return the subject to a ventilator platform that is routinely used at their site, selected at the discretion of the treating physician. It will be documented whether or not each subject completes the clinical study. If the Investigator becomes aware of any serious, related adverse events after the subject completes or withdraws from the study, they will be recorded in the source documents and on the CRF. Specific subject and study stopping rules are outlined in section 5.

5 STUDY EVALUATIONS AND MEASUREMENTS

5.1 Screening and Monitoring Evaluations and Measurements

5.1.1 Medical Record Review

- Date of birth
- Gender
- Race/Ethnicity
- Current Dosing Weight
- Gestational age
- Corrected gestational age at entry into study
- Corrected gestational age at discharge
- Birth weight

- Current medications
- SBS and WAT-1 Score
- Respiratory support required at discharge

5.1.2 Physical Examination

Cardiorespiratory assessment including respiratory rate, auscultation, symmetry, retractions, nasal flaring, and asynchrony index.

5.1.3 Vital Signs

Vital signs for the study will be recorded from the electronic medical record and continuous multiparameter clinical monitors. Any vital signs seen outside the ranges considered clinically normal for each subject will be reported to the medical team as standard practice. All bedside care team members will be aware that the subject is enrolled in the study. BP will be monitored using the standard automated device and cuff that is being used currently. HR, Pulse oximetry, Tcom will be monitored continuously as is the standard of care for ventilated children in the N/IICU and PICU.

5.1.4 Laboratory Evaluations

- Salivary cortisol samples will be collected three times per day using a swab placed in the patient's mouth to collect pooled saliva. Samples will be collected at the same time each day and independently analyzed for cortisol values. The 3 cortisol values will be averaged for the 24 hour time frame. The samples will be labeled with study ID#, date and time of collection and stored at -20C prior to being shipped for analysis.
- Samples will be shipped on dry ice to Salimetrics SalivaLab, Attn: [name] [name].
- Salivary Cortisol testing: Samples will be thawed to room temperature, vortexed, and then centrifuged for 15 minutes at approximately 3,000 RPM (1,500 x g) immediately before performing the assay. Samples will be tested for salivary cortisol using a high sensitivity enzyme immunoassay (Cat. No. 1-3002). Sample test volume is 25 µl of saliva per determination. The assay has a lower limit of sensitivity of 0.007 µg/dL, a standard curve range from 0.012-3.0 µg/dL, and an average intra-assay coefficient of variation of 4.60%, and an average inter-assay coefficient of variation 6.00%, which meets the manufacturers' criteria for accuracy and repeatability in Salivary Bioscience, and exceeds the applicable NIH guidelines for Enhancing Reproducibility through Rigor and Transparency. 10% of the samples will be run in duplicate to report an intra-assay variability.
- Blood gas values order by the medical team for clinical care will be documented and trended.

5.1.5 Ventilatory Parameters

The following parameters will be collected and trended from the ventilator:

- FiO₂
- RR

- Vt
- MAP
- PIP
- PEEP
- Dynamic Lung Compliance (Crs)
- Dynamic Lung Resistance (Rrs)
- NAVA level
- Edi peak and min - measured from the Edi Catheter that will remain in place during the 11 days of data collection
- Pressure waveform data

